6 BIOSTATISTICAL ANALYSIS

6.3 Statistical Hypothesis

The null hypothesis is that rates of COVID booster vaccination will be equal in both of the intervention groups when compared to control.

6.4 Samples size determination

Sample size estimates suggest that ~1,100 individuals in each arm will allow us to observe a 5% difference in vaccination rates compared to the usual care arm, assuming a usual care arm vaccination rate of 20% as well as assumptions of alpha=0.05 and power=0.80. Given that more than 1 million patients receive care at MGB, we expect to identify at least 5,000 patients who have not yet received the booster vaccination at the outset of the trial and who will be eligible to receive one of the messages. This will also provide sufficient power for secondary outcomes. Under the same assumptions, we should be able to observe a <6% difference in 6-week vaccination rates compared to usual care, assuming a usual care arm vaccination rate of 25%.

6.5 Statistical analyses

6.5.1 Analysis of the primary endpoint

The primary outcome will be the rate of receipt of COVID booster vaccine dose in each arm at the target primary care outpatient appointment, treated as a binary outcome. We will use logistic regression to compare outcomes between each intervention arm versus usual care and against each other. Of note, we chose not to formally adjust for multiple testing in the primary analysis for several reasons. First, although the chance of finding at least one false positive among several tests is >5%, a Bonferroni correction would be much too conservative in this case, because the multiple comparisons among the treatment arms share the same four exposure groups. Second, a recent systematic review of multiple arm trials showed that more than half of all randomized trials with multiple exposure groups do not adjust for multiple comparisons,¹⁸ reasoning that if each exposure was compared with control in a separate trial, no adjustment would be necessary.

6.5.2 Analysis of the secondary endpoints

Secondary outcomes will include in each arm the rate of receipt of COVID booster vaccine 6 weeks after the target primary care outpatient appointment. As in the primary analysis, we will use the MGB Research Patient Data Registry (RPDR) and/or Electronic Data Warehouse (EDW) for outcome measurement. We will use logistic regression to compare outcomes between each intervention arm versus usual care and against each other; in secondary analyses, we will additionally adjust for any imbalanced baseline characteristics.

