3. SUBJECT SELECTION

This study will include patient subjects for intervention and analysis. We will use the Mass General Brigham Research Patient Data Registry (RPDR) and/or Epic Enterprise Data Warehouse (EDW) to identify Mass General Brigham (MGB) patients age ≥ 18 who are eligible for the COVID booster vaccine, who have not received a dose as of the time of upcoming primary care clinic visit. We will then cross check that with the COVID-19 vaccine registry so that we can additionally exclude patients who may have received a vaccination that has not yet been entered into RPDR.

Patients will be excluded if they did not receive the full set of their primary COVID-19 series or had a severe allergic reaction to either dose of their primary series. All MGB patients who meet the criteria above will be eligible for the study. We plan to begin the study after the booster vaccine is widely available to individuals 18 years of age or older. Based on a recent survey data from the Kaiser Family Foundation, at least 45% of the fully-vaccinated population are at least somewhat skeptical about obtaining a booster vaccination.

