4. SUBJECT ENROLLMENT

4.1 Methods of enrollment

We will use the Mass General Brigham COVID-19 Vaccine Registry and Research Patient Data Registry (RPDR) and/or Epic Enterprise Data Warehouse (EDW) to identify eligible patients. The COVID-19 Vaccine Registry contains identified patient data, including the type of vaccine administered, first or second dose, as well as when and where the patient received their vaccine. The registry integrates information from vaccines administered by MGB, administrations entered into Epic based on patient report, and the state's Massachusetts Immunization Information System (MIIS) that includes vaccination sites across the state. General patient demographic information, adverse reactions and patient identifiers are included in the COVID-19 Vaccine Registry.

We will thus use the Mass General Brigham COVID-19 Vaccine Registry and EHR information in the Research Patient Data Registry (RPDR) and/or Epic Enterprise Data Warehouse (EDW) to identify MGB patients age ≥ 18 with an upcoming primary care outpatient appointment who are also eligible for the COVID booster vaccine based on routinely-collected data from these sources. We plan to launch the study after the booster vaccine has become widely available to adults and supply of vaccines at MGB is anticipated to be sufficient. Because the intervention cost is extremely low per patient, we plan to include all eligible patients.

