5.2 Overall Design

We will use the Mass General Brigham COVID-19 Vaccine Registry and EHR information in the Research Patient Data Registry (RPDR) and/or Epic Enterprise Data Warehouse (EDW) to identify all patients age ≥ 18 with an upcoming primary care outpatient appointment who are eligible for the COVID booster vaccine. We plan to launch the study after the booster vaccine has become widely available to adults over age 18 and supply of vaccines at MGB is anticipated to be sufficient. All eligible patients will be randomized to one of three arms: 1) “why” messaging, 2) “how” messaging, or 3) standard of care (“usual care”). We will conduct stratified randomization based on the primary care clinic the patient attends and day of the week the upcoming visit is on.

The primary outcome will be the rate of booster vaccination at the targeted visit. Secondary outcome will be receipt of a booster vaccine within 6 weeks of the target visit at any location. After completion of the trial, we will utilize data from the RPDR and/or EDW to develop models that predict which patients are most likely to respond to each intervention using patient baseline characteristics, which in the future could allow for targeting of interventions to specific patients. We will use the Mass General Brigham COVID-19 Vaccine Registry and the RPDR/EDW for outcome measurement.

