5.2.1 Aim 1 Design

[figure not shown]
In Aim 1 of the study, we will conduct a 3-arm randomized controlled trial to compare the effectiveness of two interventions compared to usual care on COVID-19 vaccination uptake. We will include Mass General Brigham (MGB) patients age ≥ 18 with an upcoming primary care outpatient visit with a Mass General Hospital primary care provider who are eligible for the COVID booster vaccine and who have not received a dose. This approach has been approved by MGH primary care leadership. Patients will be excluded if they did not receive the full set of their primary COVID-19 series.

Patients will be randomized equally to one of three arms: 1) “why” messaging, 2) “how” messaging, or 3) standard of care (“usual care”). We plan to conduct stratified randomization based on the primary care clinic the patient attends to account for differences in patient populations between clinics and based on the day of the week the upcoming visit is on to minimize logistic difficulties in the intervention delivery. “Why” messages will focus on reasons to get the vaccine, including protecting self and loved ones or the idea of herd immunity. “How” messages will focus on the details of obtaining a vaccination at MGB, what to expect, and how to prepare for the visit. The messages will be sent through the EHR electronic patient portal for portal users. For patients whose primary language listed in the EHR is not English, they will be offered translated messages following standard MGB Gateway messaging practices. Gateway messages will first include a message translated in their primary language (Spanish, Portuguese, Arabic, Chinese, Russian, Haitian Creole or Bosnian) followed by an English version of the message. Consistent with recent studies for influenza vaccination and the approach approved by MGH primary care leadership, we will send a message to patients a few days in advance of their office visit.¹⁶ Based on current MGH practice (i.e., standard of care), patients in Arm 3 will not receive any additional message about their upcoming visit, beyond what they already receive by MGH. **Initial examples of these messages are attached.**

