7 RISKS AND DISCOMFORTS

We believe there is no more than minimal risk involved to patient subjects, as subjects will be receiving COVID-19 booster vaccination information through routine communication methods that will encourage the uptake of a vaccine recommended by the CDC and MGB in order to prevent COVID-19 disease. The study team will not be providing any direct care to patients and all vaccination decisions will ultimately be made by the patient, with the potential consultation of their medical team at Mass General Brigham. Thus, the main potential risk to subjects in this study is related to privacy of data, and we will take several measures to ensure that this risk is minimal, and that patient information is safeguarded.

Patient data for study outcome evaluation will be drawn from the Mass General Brigham COVID-19 Vaccine Registry and EHR information in the Research Patient Data Registry (RPDR) and/or Epic Enterprise Data Warehouse (EDW). The Mass General Brigham COVID-19 Vaccine Registry is a secure repository of data containing COVID-19 vaccine administration, utilization and adverse event information for analysis by the research community. The investigators are aware of the sensitive nature of the data and are committed to protecting patient privacy. Only the minimum necessary identifiable health care data needed to achieve the intended purpose will be used. All the data in the registry is contained within the Mass General Brigham firewall, and its usage is logged and audited. It is only accessible to IRB-approved researchers.

For all study data, we will safeguard any identifiable information in accordance with IRB practices, limit access to the information to study investigators actively involved in the research who have all undergone human subjects research training, and store any data in accordance with IRB practices. Finally, as is our routine practice, great care will be taken to ensure the confidentiality of all data and to protect the privacy of participants through translation of all potentially traceable identifiers into untraceable coded subject numbers whenever possible.

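### Section 6.5.2 leaves the COVID-19 Vaccine Registry out of the outcome sources for the any-location 6-week endpoint, in conflict with Sections 2, 5.2, 5.6 and 7; followed literally, it may under-capture boosters given outside MGB

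*Combined protocol and SAP*

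**What the plan says.** Section 5.2 defines the secondary outcome as "receipt of a booster vaccine within 6 weeks of the target visit at any location" and later in the same section names the outcome sources: "We will use the Mass General Brigham COVID-19 Vaccine Registry and the RPDR/EDW for outcome measurement". Section 7 agrees: "Patient data for study outcome evaluation will be drawn from the Mass General Brigham COVID-19 Vaccine Registry", together with EHR data from RPDR and/or EDW. The endpoint justification in the Section 2 table also lists the Registry, and Section 5.6 explains the end of outcome collection by the time the Registry needs to become complete.

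Section 6.5.2, the analysis text for this endpoint, differs: "As in the primary analysis, we will use the MGB Research Patient Data Registry (RPDR) and/or Electronic Data Warehouse (EDW) for outcome measurement". Its reference back to the primary analysis settles nothing, because 6.5.1 names no data source.

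Three other places bear on the difference:

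- Section 4.1 says the Registry combines doses given by MGB, doses entered into Epic on patient report, and the "Massachusetts Immunization Information System (MIIS) that includes vaccination sites across the state". No other source is described as receiving that state feed.
- Section 3 adds a Registry check at screening in order to "exclude patients who may have received a vaccination that has not yet been entered into RPDR".
- Section 5.2.1 says that in the 'how' arm "messages will focus on the details of obtaining a vaccination at MGB". The 'why' messages give reasons to be vaccinated.

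**The concern.** The at-visit primary cannot tell an extra vaccination from one that would have been given elsewhere. The any-location 6-week endpoint is the only planned outcome that can, and only if outside doses are recorded about as well as MGB doses.

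A programmer who works from 6.5.2 could leave the Registry out in good faith. The general rule in the Section 2 table, RPDR first with EDW as a supplement, points the same way. Outside doses might then be recorded less completely than doses given at MGB. If 'how' messages lead some patients to take at MGB a dose they would otherwise have had at an outside site, that move would appear as uptake. It would affect 'how' versus usual care, and also 'how' versus 'why', which is the central contrast of Aim 1.

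**Working it through.** **1. Sources side by side.**

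| Section | Sources named or implied for outcomes |
|---|---|
| 2 (endpoint justification) | Registry, and RPDR and/or EDW |
| 5.2 | Registry and RPDR/EDW |
| 5.6 | Registry (through its lag) |
| 7 | Registry, and RPDR and/or EDW |
| 6.5.1 | none |
| 6.5.2 | RPDR and/or EDW |

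Section 6.5.2 is the exception.

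**2. The plan's own figures (Section 6.4).** For 20% versus 25%, two-sided alpha 0.05 and power 0.80, with pooled variance under the null:

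n = [1.960 × √(2 × 0.225 × 0.775) + 0.842 × √(0.20 × 0.80 + 0.25 × 0.75)]² / 0.05² = 1,094 per arm.

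This reproduces the stated figure of about 1,100. At 1,100 per arm and a 25% usual-care rate, the difference detectable with 80% power is 5.3 points, in line with the stated bound of under 6. Neither figure is affected by this point.

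**3. Bias formula.** Let T be the true 6-week rate, equal in both arms; f the outside doses in usual care, in points; m the points moved from outside sites to MGB by the 'how' message; and s the share of outside doses that the source captures.

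- Recorded rate, usual care: T − f(1 − s)
- Recorded rate, 'how': T − (f − m)(1 − s)
- Spurious difference: (1 − s) × m

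**4. Inputs.** T = 25% is the plan's assumed 6-week usual-care rate. The plan assumes 20% at the target visit, so 25 − 20 = 5 points come later or elsewhere. Taking f = 5 treats all of these as outside doses, which is the ceiling under the plan's rates, because some could be later doses at MGB. The documents give neither m nor s, so both are assumed over a range. Sample sizes are 1,100 per arm and 5,000/3 ≈ 1,667 per arm.

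**5. Probability of a false significant result.** With d the spurious difference and SE = √[p₀(1 − p₀)/n + p₁(1 − p₁)/n], the probability is Φ(d/SE − 1.96) + Φ(−d/SE − 1.96). Example with s = 0, m = 2, n = 1,100: p₀ = 0.20, p₁ = 0.22, SE = √[(0.1600 + 0.1716)/1,100] = 0.01736, d/SE = 1.152, probability 0.210.

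| Capture s | Points moved m | Recorded usual care / 'how' | Spurious difference (points) | 1,100 per arm | 1,667 per arm |
|---|---|---|---|---|---|
| 0 | 2 | 20.0% / 22.0% | 2.0 | 0.210 | 0.294 |
| 0 | 3 | 20.0% / 23.0% | 3.0 | 0.403 | 0.560 |
| 0.5 | 2 | 22.5% / 23.5% | 1.0 | 0.086 | 0.105 |
| 0.5 | 3 | 22.5% / 24.0% | 1.5 | 0.132 | 0.176 |
| 0.8 | 2 | 24.0% / 24.4% | 0.4 | 0.056 | 0.058 |
| 0.8 | 3 | 24.0% / 24.6% | 0.6 | 0.062 | 0.069 |
| 1 | any | 25.0% / 25.0% | 0 | 0.050 | 0.050 |

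Over m = 1 to 5 points at 1,100 per arm, the probability runs from 0.089 to 0.803 at zero capture, 0.059 to 0.281 at half capture, and 0.051 to 0.085 at 80% capture. All figures treat patients as independent and ignore clustering by visit day.

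**The case against.** The strongest reply is that 6.5.2 contains one sentence of shorthand. It does not say that the Registry is excluded, and four other sections name or imply it for outcomes, including the section that defines the endpoint. That stands: the defect is a conflict between 6.5.2 and the rest of the protocol. It does not remove the need for a correction, because 6.5.2 is the analysis text and does not defer to 5.2.

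A reader might go further and infer that the trial will measure the endpoint from a source the protocol itself calls incomplete, that outside boosters will be missed, and that the 'how' arm is therefore favored. The documents do not support this:

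- Section 3 describes delayed entry into RPDR at the time of screening. It says nothing of the kind about EDW.
- Section 4.1 says patient-reported doses are entered into Epic, and EDW holds Epic data (Section 5.7). Even the literal 6.5.2 would therefore capture some outside doses. Whether RPDR or EDW also receives the state feed cannot be told from the documents.
- Section 5.2.1 shows what the 'how' message says, not that patients change site because of it. Moving 2 or 3 points means moving 40% to 60% of a 5-point pool that is already the ceiling.
- The 21% and 40% figures hold only at zero capture, and the documents give no reason to choose that value.

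**Conclusion.** The conflict is real and should be corrected. Section 6.5.2 omits the one source described as integrating the state feed, for an endpoint defined as any-location. Followed literally, it may under-capture outside doses, possibly to a different extent by arm.

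The size cannot be derived from the documents. It equals the uncaptured share times the points moved. It matters when capture is poor and the shift is several points, and it is close to nothing at 80% capture or better. The probabilities rest on the plan's 20% and 25% rates, the whole 5-point remainder being outside doses, no true difference in total uptake, and no clustering.

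The point is confined to the secondary endpoint. A reader might extend it to the primary, but that outcome is a dose given at an MGH primary care visit, and nothing in the documents shows a capture problem there.

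**What to change.** Replace the source sentence in 6.5.2 with wording such as: the 6-week outcome is any booster dose dated from the target visit through 6 weeks afterwards, recorded in the COVID-19 Vaccine Registry (including MIIS) or in RPDR/EDW, with the same sources used in all arms and data extracted after the Registry lag. Add the extraction date and a rule for doses on which the sources disagree. Section 5.6 currently ends collection one month after the visit, which is shorter than the 6-week window, so it should be aligned with that date.

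A matching source statement in 6.5.1 would give the cross-reference something to point to; this is clarification only.

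The cost is a wording change and the wait for the Registry to fill. No new data are needed, because the Registry is already used for eligibility and its linkage to RPDR/EDW is described in Sections 5.7 and 9.5.

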4.3 Treatment assignment and randomization

All eligible patients will be randomized to one of three arms: 1) “why” messaging, 2) “how” messaging, or 3) “standard of care (“usual care”). We plan to conduct stratified randomization based on the primary care clinic the patient attends to account for differences in patient populations between clinics. We will also use block-stratified randomization, in which the unit of randomization is the day of the week the study visit is on. This choice was made in response to the logistical difficulties randomizing at the patient level presented. Each weekday, eligible patients will be identified that have an upcoming visit 2-3 days from then. The day of the week of that visit will be randomized in a 1:1:1 ratio with a random number generator to one of three arms: 1) “why” messaging, 2) “how” messaging or 3) “standard of care” (“usual care”).

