5.2.2 Aim 2 Design

In Aim 2, we will assess association of clinical and demographic characteristics with intervention responsiveness. To do this, we will measure baseline patient clinical, historical, and demographic characteristics. Characteristics measured from the RPDR/EDW will include age, gender, race, prior influenza vaccine history, and comorbidities that increase risk of severe COVID disease, among others. We will also measure zip-code linked variables including mean household income, education level, rurality, and prevalence of COVID in the patient's surrounding community. We will develop models that predict which patients are most likely to respond to each intervention using patient baseline characteristics, which in the future could allow for targeting of interventions to specific patients.

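### Clinic stratifies the randomisation but no clinic term is named in the primary model, and the only covariate rule adjusts for whatever turns out imbalanced

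*Combined protocol and SAP*

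**What the plan says.** **Randomisation.** Section 4.3: "We plan to conduct stratified randomization based on the primary care clinic the patient attends to account for differences in patient populations between clinics". The same section says "the unit of randomization is the day of the week the study visit is on". Section 5.2 presents clinic and day together as stratification factors: "We will conduct stratified randomization based on the primary care clinic the patient attends and day of the week the upcoming visit is on". Section 5.2.1 repeats both factors and gives the reason for the second as logistics: "based on the day of the week the upcoming visit is on to minimize logistic difficulties in the intervention delivery".

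**Primary analysis.** Section 6.5.1: "We will use logistic regression to compare outcomes between each intervention arm versus usual care and against each other". No clinic term, day term or covariate is named. Adjustment is mentioned there only in connection with multiple testing.

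**Covariate adjustment.** The one rule is in 6.5.2: "in secondary analyses, we will additionally adjust for any imbalanced baseline characteristics". The word 'additionally' implies that the base model is unadjusted. It is not clear whether the rule covers only the 6-week endpoint or also a further analysis of the primary endpoint. Section 6.5.3 plans means and frequencies at baseline, with no test or threshold for imbalance.

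**Data already planned.** Section 5.2.2 will extract "age, gender, race, prior influenza vaccine history, and comorbidities that increase risk of severe COVID disease", among others, for the Aim 2 models.

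**The concern.** There are two gaps. First, the design treats clinic as important enough to stratify on, yet the analysis does not say that clinic is used. A factor that predicts the outcome and is left out of the model costs precision. Where arms are not balanced within clinic, leaving it out can also make ordinary standard errors too small.

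Second, the 6.5.2 rule selects on the wrong property. A chance difference in a variable unrelated to vaccination triggers adjustment; a strong predictor that happens to be balanced does not. With no definition of imbalance, two analysts following the text could fit different models, and that choice would be made after baseline differences are known. At stake are some precision in the main comparison and the credibility of the adjusted results.

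**Working it through.** **1. The plan's own figure.** Section 6.4 gives about 1,100 per arm for 20% vs 25%, alpha 0.05, power 0.80. The two-sided pooled-variance formula for two proportions gives 1,094 per arm, and power at 1,100 is 0.802. The figure reproduces as an unadjusted, individually randomised comparison and is not disputed. The 5,000 patients expected in 6.4 give 5,000/3 = 1,667 per arm.

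**2. Precision from a clinic term (patient-level formula).**

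Power = Φ(0.05 / √[(0.20×0.80 + 0.25×0.75)(1 − R²)/n] − 1.96), with R² = SD²/(0.225×0.775).

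The documents give no between-clinic spread, so the SD is an assumption.

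| Between-clinic SD | R² | Power, n=1,100 | Gain (points) | Power, n=1,667 | Gain (points) |
|---|---|---|---|---|---|
| none (no clinic term) | 0 | 0.803 | – | 0.934 | – |
| 3 points | 0.0052 | 0.805 | 0.2 | 0.935 | 0.1 |
| 5 points | 0.0143 | 0.809 | 0.6 | 0.937 | 0.3 |
| 10 points | 0.0573 | 0.826 | 2.3 | 0.946 | 1.2 |

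**3. Adding one prognostic covariate (simulation).** 6,000 two-arm trials per row; 15 clinics assumed; patient-level allocation balanced within clinic. The gap is the assumed difference in vaccination rate by influenza-vaccination history. Power (%) is unadjusted / clinic / clinic plus influenza history.

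| SD, gap (points) | n=1,100 | n=1,667 |
|---|---|---|
| 3, 10 | 80.4 / 80.6 / 81.0 | 93.2 / 93.4 / 93.7 |
| 5, 10 | 80.7 / 81.2 / 81.8 | 93.5 / 93.7 / 94.0 |
| 5, 20 | 79.7 / 80.2 / 82.4 | 93.0 / 93.2 / 94.5 |
| 10, 20 | 75.7 / 77.6 / 79.9 | 89.9 / 90.9 / 92.7 |

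These show the gain from adjustment. They are not this trial's power, because 4.3 randomises days.

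**4. What the imbalance rule does.** With 10 independent covariates (assumed) and p<0.05 as the criterion, the chance of flagging at least one is 1 − 0.95¹⁰ = 40%. With a standardised difference above 0.1 in one pairwise comparison, each covariate is flagged with probability q = 2Φ(−0.1/√(2/n)), and 1 − (1 − q)¹⁰ is 17% at 1,100 and 4% at 1,667. The unstated threshold therefore changes the model. In a simulation with one prognostic and nine noise covariates (1,100 per arm, 1,500 trials per row), the p<0.05 rule picked the prognostic one in about 5% of trials. Power for unadjusted / pre-specified prognostic adjustment / imbalance-selected was 0.80 / 0.82 / 0.80 at a log odds ratio of 0.5 per SD, and 0.82 / 0.86 / 0.82 at 1.0.

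**5. Type I error without a clinic term.** Null simulations with 15 clinics and 3,300 patients (assumed), no day effect, ordinary standard errors:

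| How days are drawn | Enrolment | Error at SD 3 / 5 / 10 points |
|---|---|---|
| One draw shared by all clinics | 1 week | 0.054 / 0.052 / 0.050 |
| 2:2:1 within each clinic | 1 week | 0.062 / 0.067 / 0.117 |
| Blocks of three days within clinic | 1 week | 0.058 / 0.063 / 0.101 |
| Blocks of three days within clinic | 4 weeks | 0.041 / 0.053 / 0.044 |
| Independent clinic-day draws | 1 week | 0.083 / 0.130 / 0.286 |
| Independent clinic-day draws | 4 weeks | 0.052 / 0.063 / 0.116 |

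Repeat runs put the last two rows at about 0.07–0.29 and 0.05–0.11, the same within simulation error. With a clinic term the error was about 0.04–0.06 throughout.

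Cross-check for independent draws: one week has 15×5 = 75 clinic-days of 3,300/75 = 44 patients. The design effect is 1 + 43×SD²/0.16 = 1.24, 1.67, 3.69, and 2Φ(−1.96/√DE) = 0.079, 0.130, 0.307. Four weeks has 300 clinic-days of 11 patients: 1 + 10×SD²/0.16 = 1.06, 1.16, 1.63, giving 0.057, 0.068, 0.124. Both agree broadly with the simulation.

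**The case against.** The best defence is that the plan is adequate as it stands. Section 6.5.1 compares rates by arm and 6.5.2 adjusts additionally, so an unadjusted main model is implied, and that is a legitimate choice. The precision gain is small, and at 1,667 per arm the nominal patient-level power is already 93%. An SD of 10 points around a rate near 20% is a large spread for the primary care clinics of one hospital. The 40% figure rests on ten independent covariates and a p<0.05 rule, neither of which is in the documents. Adding covariates also changes the odds ratio from marginal to conditional, although the endpoint is a rate.

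Most of this stands and limits the point. It does not rescue the 6.5.2 rule, which stays undefined and selects on the wrong property, and it gives no reason to leave clinic unused when it is known at randomisation. The estimand remark is met by reporting a standardised risk difference.

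A reader might infer three stronger things that the documents do not support:

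- *That the primary comparison is biased.* Omitting a baseline covariate from a randomised comparison does not do that.
- *That the trial's type I error is as high as 0.29.* That needs independent draws for every clinic-day, one week of enrolment and a 10-point SD. Section 4.3 does not say how clinic and day combine. Its description of identifying patients each weekday suggests rolling enrolment, while the one-week limit in 5.6 may refer to each patient or to the whole trial.
- *That 1,100 per arm is wrong because of this.* It reproduces, and this fix needs no more patients.

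**Conclusion.** The point holds as a low-cost improvement that should be made, not as a flaw that invalidates the trial. Certain from the text: clinic is a stratification factor, the primary model names neither clinic nor any covariate, and the sole adjustment rule is undefined and data-driven.

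The size of the precision loss rests on assumed clinic spread and covariate strength. Clinic alone is worth about 0.2 to 2.3 points of power at 1,100 per arm and 0.1 to 1.2 at 1,667; clinic with a prognostic covariate is worth roughly half a point to four points at 1,100. The surer benefit is an adjusted analysis that does not depend on choices made after the data are seen.

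The type I error effect is conditional on the allocation scheme: about 0.07–0.29 over one week and 0.05–0.11 over four weeks for independent clinic-day draws, and little or none with a shared draw or with blocking over several weeks. All these figures assume no day effect. Clustering by visit day and the way days are allocated are separate and larger issues that covariate adjustment does not solve.

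**What to change.** In 6.5.1 and 6.5.2:

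1. Pre-specify the logistic model for both endpoints as arm, clinic and a short fixed list from 5.2.2: age, gender, race in fixed categories, prior influenza vaccination (yes/no) and any comorbidity on a named list (yes/no).
2. State how small clinics are pooled and how missing record values are handled, both fixed before outcome data are seen.
3. Delete adjustment for imbalanced characteristics. Keep the unadjusted comparison as a sensitivity analysis for both endpoints.
4. Report the covariate-standardised (marginal) risk difference beside the odds ratio, since the endpoint is a rate and the adjusted odds ratio is conditional.

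The cost is a little more SAP wording and analysis work, chiefly the pooling rule, the comorbidity list and the missing-value rule. Clinic is known at randomisation and the covariates are already to be extracted, so no extra patients or data are needed. Standard errors that respect visit-day clustering must be settled separately.
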